## Baseline data

In the privacy of the participant's home or a preferred private location, baseline data were collected and included demographic data (such as age, education, income, and medical history) and manual measurements (such as blood pressure, height, and weight), along with a series of study questionnaires (such as the Hill-Bone Compliance to High Blood Pressure Therapy Scale, Self-Efficacy for Managing Chronic Disease, Healthcare Utilization, and the Self-Care of Hypertension Inventory). To manage data, a secure, web-based application called the Research Electronic Data Capture (REDCap) was used to record data via an iPad. The REDCap System provided a secure web-based application using a Cloud provider. If REDCap was not operational, data were collected by paper and pencil and later recorded in REDCap.

## Baseline Measures

### ***Screening Questions and Physical Activity Readiness Questionnaire (PAR-Q).***

Screening questions reflected the eligibility criteria for inclusion and exclusion in the study. The 2017 PAR-Q+ was used as a screening tool to assess possible exercise safety risk before the start of a physical activity program (Warburton et al., 2017). Answers were based on specific health history questions (Warburton, Gledhill, et al., 2011). Sensitivity and specificity of the PAR-Q+ in individuals with and without HTN was 0.90 and 1.0 respectively, and reliability was 0.99 (Warburton, Bredin, et al., 2011).

***Demographic Data Tool.*** The PI developed the Demographic Data Tool to collect standard information not addressed on the other instruments and important in describing the sample. The tool included information such as age, education, income, and medical history.

## Baseline and Repeated Measures

**Manual Blood Pressure.** Using a home BP monitoring procedure (Muntner et al., 2019), participants were seated quietly for at least 5 minutes with their back supported and feet flat on the floor. A manual BP measurement was taken with a Welch Allyn Tycos (DS58) hand aneroid sphygmomanometer in the bare left upper arm while supported at heart level. Three consecutive BP measurements were taken, one minute apart and averaged (Pickering et al., 2005; Whelton et al., 2018). Manual BP measurements were taken at baseline and then at month 3, 6, and 9 to verify readings from the digital Omron oscillometric BP monitor used for the technological data in the study (Abel & DeHaven, 2021). To maintain consistency with the Omron BP recommendation, the left upper arm was used for BP measurements (Omron Healthcare, 2015a).

**Body Mass Index.** A portable platform Seca 813 electronic scale was used to measure weight in pounds. Height was measured using a portable Seca 217 stadiometer with measurements to the nearest 0.1 centimeter. Weight and height data were used to calculate the body mass index (BMI) using the metric system formula, weight in kilograms divided by height in meters squared, expressed as: weight (kg) / [height (m)] (*Healthy weight: Body mass index*, 2015).

**Waist Circumference.** Waist circumference was measured to the nearest 0.1 cm. by using a soft Gulick tape measure to circle around the waist at the top of the iliac crest and slightly above the level of the umbilicus from the “0” end of the tape to the intersection of the waist measurement number. The Gulick tape measure includes a mechanism to ensure consistent tension when measuring. The participant stood in an upright position without sucking the abdomen in while the tape was pulled taut without squeezing into the skin (Frey, 2019, September, 2; "Waist measurement," n.d.).

**Hill-Bone Compliance to High Blood Pressure Therapy Scale (Hill-Bone CHPPTS).** The Hill-Bone CHPPTS was designed to assess medication compliance/adherence (Kim et al., 2003). The scale is a 14-item assessment tool is a 14-item tool designed to assess medication compliance/adherence. Of the tools three subscales, this study focused on medication taking, 8-items plus one item that addressed prescription refills totaling 9-items. Responses are scored on a 4-point Likert scale from 1 = none of the time to 4 = all of the time. Scores ranged from 9 to 36 and the minimal score indicated perfect adherence. Cronbach's alpha for the Hill-Bone CHPPTS medication compliance subscale was .77, and the total scale was .75 (Kim et al., 2000).

**Self-Efficacy for Managing Chronic Disease (SEMCD).** The SEMCD is a 6-item scale used to measure perceived ability to manage salient aspects of life with chronic disease such as symptom control, role function, and emotional functioning (Lorig et al., 2001). Responses are scored on a 10-point numeral rating scale (1= not at all confident to 10 = totally confident) with higher values indicating self-efficacy. For the SEMCD, the Cronbach's alpha across eight studies ranged from .88 to .91 (Ritter & Lorig, 2014).

**Healthcare Utilization.** Healthcare Utilization is a 4-item tool used to measure the number of times a health care service is used. Responses are single item numbers and self-reported by participants. Test-retest reliability for Healthcare Utilization ranges from .76 to .97 (Lorig et al., 1996).

**Communication with Healthcare Provider.** Communication with Physicians is a 3-item scale used to monitor changes in the key behaviors taught in the CDSMP with items related to prepared questions, understanding treatment, and personal problems. Responses are recorded on a Likert scale (from 0 = never to 5 = always), scored, and averaged. A higher score indicates better communication with providers. Internal consistency reliability for the Communication with Physicians scale is .73 (Lorig et al., 1996).

**The Self-Care of Hypertension Inventory (SCHI).** The SCHI is a 23-item tool designed to measure self-care intervention effectiveness and self-efficacy in self-care. The SCHI consists of three subscales: self-care maintenance, 11 items; management, 6 items; and confidence, 6 items (Dickson et al., 2016). Each subscale has a differently worded 4-point Likert scale ranging from 0 to 4. Each subscale was scored separately and then transformed to a standardized score that ranges from 0 to 100. Scores of 70 or greater indicate self-care adequacy. Internal consistency reliabilities for the SCHI three subscales are .83 for maintenance; .78 for management; and .94 for confidence (Silveira et al., in press).

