## Recruitment

Women were recruited from Black church congregants that are known to have a high proportion of Black females, from businesses such as hair salons, Black sororities, and community events. Recruitment methods included flyers, announcements on websites using the flyer, presentations, follow-up phone calls, and face-to-face meetings with church leaders, congregants, business owners, sororities, and community members. Those interested in participating in the study were instructed to contact the research staff (PI or trained RAs) who are registered nurses, via telephone or email. The PI or RA conducted either a face to face or telephone screening interview. After an explanation of the study and answering questions, potential participants were (1) screened for inclusion/exclusion; (2) uncontrolled BP (systolic and/or diastolic greater than or equal to 130/80 but less than 160/100 mmHg; interviewees had their BP checked and reported the numbers when called for screening; BP was taken later to confirm eligibility before the consent form was signed and baseline data collected); and (3) ability to participate in physical activity using the Physical Activity Readiness Questionnaire (PAR-Q). Those who were eligible and agree to participate in the study were visited by the PI or RA at their home or another preferred private location. At that time, the participants BP was taken to confirm eligibility for the study. If the BP criteria was met, the participant provided informed consent and baseline data were obtained. If the BP criteria were not met, participants were thanked for their time and told that any collected information during the screening process would be discarded by shredding.

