## Fitbit Monitoring

With smart monitoring of connected devices in Fitbit Plus, data were tracked, analyzed, and transparently displayed to provide opportunities for participants to better understand their condition and self-manage by being actively engaged in their own care. In the CDSMP, all participants were taught to write action plans and report if they were successful, partially successful, or not successful in achieving their plan based on participant self-tracking of their data. Fitbit Plus allowed real-time adherence tracking. If participants were adhering to their action plan, study measures displayed a green color indicating a positive trend and if they were not adhering, measures would display a red color indicating a negative trend, alerting the PI to communicate with participants and encourage active engagement in their self-care.

Only the treatment arm action plans were monitored with individualized coaching messages (ITEC) via secure text messaging in the Fitbit Plus dashboard with real-time participant feedback. Coaching messages focused on helping participant's problem-solve barriers to goal

achievement with relevant dialogue to encourage BP control, medication adherence, and lifestyle modifications (physical activity, caloric intake, and weight management). The PI sent tailored ITEC messages via Fitbit Plus to treatment arm participants weekly for months 1-3, biweekly for months 4-6, and no ITEC messages for months 7-9 (to assess for sustainability).

During months 1-3, the control arm received usual care only, along with monthly manual BP and weight measures. After that time, the control arm was given the same wireless tools and apps as the treatment arm. In addition, they received individualized instruction equivalent to the treatment arm and practiced using the tools during a two-week trial period. For months 4-9, the control arm was monitored with IT via Fitbit Plus with no coaching. Fitbit Plus was used only to track participants for comparative data with the treatment arm. The control participants were not contacted between data collection periods, except to send reminders if they were not participating in daily measures.

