All baseline manual measurements and study questionnaires were repeated at 3, 6, and 9 months. All other data were collected through the Fitbit Plus Platform via wireless tools. Personal contact every three months for about 30 minutes provided a human element to the Fitbit Plus technology component and allowed the PI to troubleshoot any problem areas or equipment issues.

Gift cards were given to participants for time expended for baseline assessment (\$20) and repeated measures at 3- (\$30), 6- (\$40), and 9-months (\$60) totaling \$150.

If study participants completed all parts of the research study, then as a completion bonus, they were allowed to keep all measurement tools including the blood pressure monitor, Fitbit, and weight scale, along with the CDSMP book at the conclusion of the study. After Fitbit Plus access ended, participants were able to continue to monitor themselves through the corresponding apps on their smartphone. For those study participants who do not complete the study, the blood pressure monitor, Fitbit, weight scale, and book were returned to the PI when they exited the study.

At the completion of the study, Fitbit Plus transmitted a copy of all collected data at the request of the PI. Both the PI and study participants instructed Fitbit Plus to delete all study participant data when the study ended.

A summary of the overall results of the project in ‘lay’ language was shared with participants in their preferred format (such as email, letter, or in-person) while ensuring confidentiality of individual responses after the study has ended.

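### Manual aneroid BP is the only BP both arms share at all four time points, and the plan leaves open that the coaching PI, who knows the arm, takes the follow-up readings

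*Combined protocol and SAP*

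**What the plan says.** **Instrument and schedule.** The section Baseline and Repeated Measures states: "A manual BP measurement was taken with a Welch Allyn Tycos (DS58) hand aneroid sphygmomanometer". On timing and purpose it says: "Manual BP measurements were taken at baseline and then at month 3, 6, and 9 to verify readings from the digital Omron" monitor. Fitbit Monitoring confirms the schedule: "All baseline manual measurements and study questionnaires were repeated at 3, 6, and 9 months".

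**Control arm.** Fitbit Monitoring: "During months 1-3, the control arm received usual care only, along with monthly manual BP and weight measures". Controls get the wireless devices only after that period.

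**Coaching.** Same section: "The PI sent tailored ITEC messages via Fitbit Plus to treatment arm participants weekly for months 1-3". Messages continue every two weeks in months 4-6 and stop for months 7-9.

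**Quarterly contact.** Straight after the sentence on repeated measures, the text describes personal contact every three months, which "allowed the PI to troubleshoot any problem areas or equipment issues".

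**Staff.** Recruitment refers to "research staff (PI or trained RAs) who are registered nurses". The visit that confirms eligibility and collects baseline data is made by either the PI or an RA.

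**Analysis.** The Statistical Analysis Plan describes a mixed-effects repeated measures model, a constrained longitudinal model where appropriate, and paired t-tests of BP change in each group from baseline to month 3, 3 to 6, and 6 to 9. It does not say whether manual or Omron BP is analysed.

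The documents do not mention blinding or a separate outcome assessor, and do not say who takes BP at months 3, 6 and 9.

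**The concern.** BP control is the first specific aim. An aneroid gauge gives whatever value the observer decides on, so a reader who knows the arm and has an interest in the coaching can shift readings without meaning to. If that shift differs between arms, it adds directly to the estimated arm difference.

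The stated safeguards are a rest period, a standard posture and the average of three readings. These reduce random error, but they do not remove a shift common to all three readings by one observer. The SAP's sensitivity analyses (GEE and EM imputation) address missing data, and none would reveal a reading error that depends on arm. A favourable month-3 result in manual BP would therefore be hard to defend.

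**Working it through.** **Step 1. Which BP exists in which arm?** From Technology, Fitbit Monitoring and Baseline and Repeated Measures:

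| Time | Manual, treatment | Manual, control | Omron, treatment | Omron, control |
|---|---|---|---|---|
| Baseline | yes | yes | no | no |
| Months 1-3 | month 3 | monthly | yes | no |
| Month 6 | yes | yes | yes | yes |
| Month 9 | yes | yes | yes | yes |

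Equipment is issued after randomization, so neither arm has an Omron baseline. A change from baseline to month 3 on one instrument in both arms can come only from manual BP. At months 6 and 9 an automated device value exists in both arms.

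**Step 2. Which readings are exposed?** The protocol places baseline before the CDSMP and randomization after it. On that text only the month 3, 6 and 9 readings can be affected by knowledge of the arm.

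**Step 3. The plan's sample size.** 5/45 = 11.1% attrition; 80/0.89 = 89.9, rounded up to 90. The target of 90, with 40 per arm analysed, reproduces. It does not bear on this point except to supply n = 40.

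**Step 4. Illustration of size.** The documents give no BP SD, no correlation and no bias. Assumptions: systolic SD 12, 14 or 16 mmHg; correlation with baseline 0.5; 40 per arm; one follow-up visit adjusted for baseline; two-sided 0.05 test; true effect zero; differential reading error b.

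- SE = SD × √(1 − 0.5²) × √(2/40)
- False-positive rate = Φ(b/SE − 1.96) + Φ(−b/SE − 1.96)

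| SD (mmHg) | SE (mmHg) | b = 0 | b = 2 | b = 3 |
|---|---|---|---|---|
| 12 | 2.32 | 5% | 13.8% | 25.2% |
| 14 | 2.71 | 5% | 11.4% | 19.8% |
| 16 | 3.10 | 5% | 9.9% | 16.2% |

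Worked case, SD 12 and b = 2: b/SE = 2/2.32 = 0.86; Φ(−1.10) + Φ(−2.82) = 0.136 + 0.002 = 0.138.

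If the same error affected all three follow-up visits and their mean were analysed (all correlations 0.5), the variance factor would be (1 + 2×0.5)/3 − 0.5² = 0.417. SE would be SD × √0.417 × √(2/40) = 1.73 to 2.31 mmHg, and b = 2 would give about 14% (SD 16) to 21% (SD 12).

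**The case against.** **Manual BP is only a check on the device.** Its stated purpose is "to verify readings from the digital Omron oscillometric BP monitor", and Fitbit Monitoring foresees device data for comparing the arms. The constrained model might also accommodate an outcome with missing baselines. This has force for months 4-9. It does not help at month 3, because controls have no Omron data by then and no model can supply them.

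**Nobody says the PI took the readings.** Correct. A reader might infer it from the PI's quarterly contact, but that sentence mentions only troubleshooting. Nor did the PI see device data from every participant throughout, since controls had no devices in months 1-3. The point is only that the plan does not prevent the coach from measuring.

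**A positive BP result could never be told apart from assessor bias.** This stronger reading fails. Both arms have Omron data from month 4, so a check that does not depend on a staff observer is possible at months 6 and 9. The plan simply does not provide for it.

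**The illustration has no basis in the documents.** The bias of 2 or 3 mmHg is indeed assumed. It is also tempting to read the planned effect of 0.205 as a standardised mean difference, which would make 2 mmHg equal to 2/(0.205 × 16) = 61% up to 2/(0.205 × 12) = 81% of it. That reading does not fit the stated 80% power. With 40 per arm and correlations of 0.5, it gives 18% power for one baseline-adjusted visit and 30% for the mean of three. Taken as Cohen's f (d = 2 × 0.205 = 0.41), the mean of three visits gives 79% to 81% for correlations of 0.3 to 0.5. The metric is not stated, so no share of the planned effect is claimed here.

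**The trial looks largely complete.** The SAP reports seven early dropouts and findings on missing data, while Description of the Study is partly in the future tense. If visits are over, changes to measurement come too late, and only disclosure and analysis remain.

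**Conclusion.** The concern holds in limited form. Manual aneroid BP is the only BP both arms have at all four time points. It is observer-read, and nothing keeps the coaching PI, who knows the arm, from taking the post-randomization readings. The month-3 contrast is the most exposed; months 6 and 9 can be partly checked with device data.

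The documents show neither that bias occurred nor its direction or size. Under the stated assumptions, a 2 mmHg differential error would raise the single-visit false-positive rate from 5% to about 10%-14%. With no differential error it stays at 5%. This is a cheap improvement to protection and reporting; it does not show that the BP result is wrong.

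**What to change.** 1. **Visits still to be held, if any.** Have a trained RA who sends no coaching and is not told the arm take the manual reading. Alternatively, record the automated three-reading Omron average at the visit in both arms; at month 3, controls can use the unit about to be issued to them.
2. **At any stage.** Fix in the SAP a sensitivity analysis of the arm difference in Omron BP at months 6 and 9, adjusted for manual baseline BP, with the averaging window defined in advance. Report it beside the manual result whatever it shows, and do not switch the outcome on the basis of the data.
3. **Disclosure.** State who took each follow-up reading and whether that person knew the arm. If the coaching PI took the month-3 readings, describe that contrast as unprotected against observer bias.

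**Cost.** Some protocol wording, a few minutes at any remaining visit, and one analysis of data already being collected. The RAs and monitors already exist, although the documents describe RAs only in recruitment and baseline work, so scheduling them for follow-up may be a constraint. Blinding will be imperfect because participants may reveal their arm.

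**Limit of the Omron check.** These are home self-measurements, entered by hand in Fitbit Plus by Android users, and treatment participants have used the device three months longer. Agreement would support the manual result; disagreement would not by itself prove assessor bias.

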### **Chronic Disease Self-Management Program (CDSMP)**

After collecting baseline data, all participants were enrolled in a 6-week Chronic Disease Self-Management Program (CDSMP) that was held in a classroom at a local church. The CDSMP focused on disease management skills related to decision making, problem-solving, and action planning with topics for healthy living (such as assessing nutritious foods, improving physical activity, managing excess weight, reducing stress, adhering to medications, communicating with providers, and dealing with depression). Participants received a copy of the book entitled, *Living a Healthy Life with Chronic Conditions*, 4th Ed. with reading assignments to prepare for weekly sessions.

As a standardized curriculum, fidelity was maintained through the use of trained leaders who followed teaching materials without modifications to provide consistent and specific interventions to all participants. The CDSMP was conducted by two trained people - a nurse and a layperson (peer) with the hypertension diagnosis, who served as a role model to participants and was able to address non-medical concerns. The PI was a registered nurse who completed the CDSMP training along with the layperson who had the hypertension diagnosis. The trained layperson received an incentive/fee for working with the PI to conduct the CDSMP classes. The layperson was not a member of the research team.

Participants attended weekly 2½-hour classes for six weeks. The group size was uniform per the CDSMP recommendation for 10-16 participants per session with six classes scheduled to accommodate the 90 participants. In addition to class activities, participants made specific action plans each week that were consistent with the study aims. For example, a physical activity action plan may specifically address, “what” (this week, I will walk), “how much” (around the block),

“when” (before lunch), and “how often” (three times). All participants continued to receive usual care for HTN throughout the study period.

## Technology

After completing the CDSMP sessions, study participants were randomly assigned to either the treatment (ITEC) or the control arm (IT).

The technology component of the study was linked to Fitbit Plus, a cloud-based collaborative care platform that was designed to store and track data. The PI was trained in the Fitbit Plus platform, synchronizing data collection devices, instructing participants in the use of equipment, monitoring participant data, and interactive coaching messages. In the privacy of their homes, or another preferred location, each study participant received individualized instruction (about 45 to 90 minutes) to Fitbit Plus and all study tools accommodating various technological skills.

Study equipment included three wireless tools (Omron BP monitor, Fitbit activity tracker, and Fitbit weight scale) and five apps (Omron Connect, Fitbit, MyFitnessPal, Apple Health if iPhone user or Google Fit if android user, and Fitbit Plus). Apps were installed and tools synchronized to the participant’s smartphone. Apple Health and Google Fit allowed Fitbit Plus to import app data from Fitbit, MyFitnessPal, and Omron. Participant action plans were set up in Fitbit Plus to correspond to the study aims. As participants wore their Fitbit activity tracker, took their BP, stepped onto the weight scale, or entered food intake, their measurement data were transmitted in real time via Wi-Fi and Bluetooth Smart technology to the Fitbit Plus dashboard. In the dashboard, participants could view their data along with the PI. Two exceptions were the manual BP recording for Android users and the manual self-reported medication-taking for all participants, as described under Fitbit Plus Measures. The PI monitored all study participant data during a two-week trial period to allow participants an opportunity to adapt to using the wireless tools and apps. Once the orientation period was over, data were monitored via the Fitbit Plus platform for study purposes.

